5.2 KEY DEFINITIONS

5.2.1 Study Day

Study Day 1 is defined as the randomization day i.e. the day of first study drug administration. Subsequent days are numbered consecutively (Day 2, Day 3, etc.). Before the day of first study drug administration, study days will be numbered sequentially with negative values (i.e., Day -1, Day -2, etc.).

5.2.2 Baseline Values

Baseline values will be taken as the last non-missing assessments before dosing with study drug.

5.3 DATA HANDLING CONVENTIONS

5.3.1 Missing Data

Unless otherwise stated no imputation will be done for the missing data values. For the participants who are discontinued from the trial, all data until the point of discontinuation will be used in the summary and analyses. Reason for discontinuation will be presented in participant data listing and disposition table.

Data that are potentially spurious or erroneous will be examined using standard data management procedures and data queries will be issued prior to database lock and statistical analysis.

The Following rules will be followed for handling partial/missing date information for prior and concomitant medications:

Partial dates for medications will be imputed to decide if a medication is to be considered prior or concomitant (please refer to section 6.4 for definition of prior and concomitant medications).

Partial start dates in prior and concomitant medications will be imputed with a conservative algorithm, to the first day of the month (if missing day) or the first month of the year (if missing month). Partial end dates in prior and concomitant medications will be imputed to the last day of the month (if missing day) or the last month of the year (if missing month).

If end date of medication is missing, then medication will be considered concomitant. If start date of medication is missing and the end date is on or after the first dose of study drug or the medication is ongoing, then medication will be considered concomitant.

5.3.2 Visit Windowing

Data will be analyzed using the nominal visit i.e. study visit and analysis visit will be similar. Unscheduled visits will be listed, but not mapped to a specific analysis visit.

5.3.3 Pooling of Sites

Data from all the sites will be pooled for analysis and summarization.

6 STUDY PARTICIPANTS

6.1 DISPOSITION OF PARTICIPANTS

The following participant data will be summarized for each dose group and overall for all screened participants:

- Participants screened (i.e. all participants who signed informed consent).
- Screen failure participants and reasons for screen failure
- Participants randomized
- Participants in each analysis population
- Participants who received the booster dose
- Participants who are early terminated and reasons for early termination.

All disposition data will also be listed.

6.2 DEMOGRAPHICS AND BASELINE CHARACTERISTICS

Descriptive statistics of the demographic and baseline characteristics for each dose group and overall will be presented for safety analysis set. The following demographic and baseline characteristics will be summarized:

- Age at the time of informed consent (years)
- Sex
- Childbearing potential and reason for no childbearing potential
- Ethnicity
- Height at screening (cm)
- Weight at screening (kg)
- Body Mass Index (BMI) at screening (kg/m²)
- COVID-19 Test Result at screening (Positive, Negative)
- HBsAg Test Result at screening (Positive, Negative)
- HCV Test Result at screening (Positive, Negative)
- HIV Test Result at screening (Positive, Negative)

All demographic and baseline data will also be listed.

6.3 MEDICAL HISTORY AND VACCINATION HISTORY

Medical history will be coded with Medical Dictionary for Regulatory Activities (MedDRA) version 23.1.

Medical history (including vaccination history) data will be summarized using counts and percentages by System Organ Class (SOC), Preferred Term (PT) by dose group and overall for the safety analysis set. A participant will only be counted once in an SOC and an SOC/PT combination. All medical history data will also be listed.

6.4 PRIOR AND CONCOMITANT MEDICATIONS

Prior and concomitant medications will be coded using the World Health Organization-Drug Dictionary (WHO-DD) B3 September 2020.

Prior medications are defined as medications that started and stopped before the date of first dosing. Any medication that started on the date of dosing will not be considered prior. Any medication that stopped on the date of dosing will be considered prior.

Concomitant medications are defined as all medications (excluding study treatment) that started on or after the date of first dosing. This also includes medications ongoing on the first dosing date. Medications that started before the date of dosing and are ongoing after the date of dosing will be considered as concomitant.

For the rules to be used for handling missing or partial dates refer to Section 5.3.1.

Prior and concomitant medications will be summarized for each dose group and overall with the number and percentage of participants receiving medication by ATC class and preferred term (PT) for the safety analysis set. Medications will be sorted in alphabetical order of ATC Level and then decreasing PT frequency in overall column. A participant will only be counted once within a given ATC level and an ATC/PT combination.

All medications will be listed with ATC class, preferred term and reported medication name.

6.5 CONCOMITANT PROCEDURES

All data related to concomitant procedures a participant received during the study will be presented in a participant data listing.

6.6 TREATMENT EXPOSURE

Number of doses taken will be summarized by dose groups and overall for the safety analysis set. In addition, exposure to study drug will be summarized and will be calculated as:

Exposure duration = (Date of last dose of study drug - Date of first dose of study drug) +1

7 SAFETY ANALYSES

Safety analysis will be carried out using the safety analysis set.

7.1 ANALYSIS OF PRIMARY SAFETY ENDPOINT

7.1.1 Solicited Adverse Events within 7 days after vaccination

Solicited AEs will be collected in the eDiary by the participant for 7 consecutive days after each vaccination, starting on the day of vaccination. Solicited AEs will be graded by the investigator according to the FDA's Toxicity Grading Scale for Healthy Adult and Adolescent Volunteers Enrolled in Preventive Vaccine Clinical Trials. The following solicited reactions will be assessed:

Solicited injection site reactions: These include injection site pain, itching, tenderness, redness and swelling/induration.

Solicited systemic reactions: These include fever/body temperature, fatigue, headache, nausea/vomiting, muscle pain.

All fever measurements should be recorded by the participant in the participant diary including the first value that shows a return to normal body temperature. Oral body temperature $\geq 38.0^{\circ}\text{C}$ is defined as fever. If more than one body temperature value is recorded in the participant diary on a given day, the highest daily temperature reading will be recorded in the eCRF.

The number and percentage of participants with solicited injection site and systemic AEs within 7 days after vaccination along with the exact 95% Clopper-Pearson confidence interval (CI) for all AE rates will be presented for each dose group and overall. Differences between the dose groups will be assessed for significance using Fisher-Freeman-Halton exact test and p-values will be presented for this test. If the overall group difference is statistically significant then multiplicity adjusted p-values (using Hochberg method) for pairwise group differences will be calculated for Fisher's exact test.

Solicited AEs will also be summarized by severity grades. If a participant has the same reaction with multiple severity grades then the most severe grade will be counted.

All data for solicited adverse events will also be presented in participant data listings.

Booster Phase:

The number and percentage of participants with solicited injection site and systemic AEs within 7 days after booster vaccination along with the exact 95% Clopper-Pearson confidence interval (CI) for all AE rates will be presented. Solicited AEs will also be summarized by severity grades. If a participant has the same reaction with multiple severity grades then the most severe grade will be counted.

Duration of solicited injection site reactions and solicited systemic reactions after booster dose will also be summarized. In case of missing end date for a reaction after booster dose the last available date of reaction will be considered as the end date in calculation of the duration. Duration for a reaction will be calculated as: (Last occurrence date of reaction after booster – start date of occurrence of reaction after booster +1).

All data for solicited adverse events in the booster phase will also be presented in participant data listings.

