## STATISTICAL ANALYSIS

### Sample size justification

No formal sample size calculation has been performed. A total of 150 Participants is considered sufficient to obtain initial safety data for VLA2001, especially since inactivated vaccines are a well-established, safe vaccine technology. Fifty Participants per group will allow for 95% confidence that an AE with a true underlying incidence of about 2% would be observed in the present study.

For the Booster Phase of this study, no formal sample size calculation has been performed and no minimal or maximal number of participants is defined. Based on operational considerations the total number of participants is expected to be up to approximately 80.

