## **8.5 Rationale and Justification for the Booster Phase.**

Following the successful completion of the Part A primary analysis (Day 36), the high dose was found to be the optimal dose as defined in the primary objective of the study. Based on the assessed comparable safety and superior immunogenicity results at Day 36, the high dose has been selected for further clinical development. Valneva has decided to extend the VAL2001-201 study, by investigating the effects of a Booster dose at 8-9 months after completion of the primary immunization schedule with VLA2001. The booster dose will be offered to all participants who do not meet an exclusion criteria regardless of their initial response to the primary immunization schedule in the different dose groups. Hence, the effect of a booster dose will be studied in a population with different levels of pre-existing antibody levels against SARS-CoV-2.

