### **8.5.1 Possible Benefits for Participant**

This is a first-in-human study, therefore the clinical benefits of VLA2001 have not yet be established. The overall benefit and risk balance for individual participants in the study cannot be ascertained.

An initial analysis of the data up to Day 36 from this study has shown that VLA2001 is generally safe and well tolerated across all dose groups tested, with no safety concerns identified by an independent Data Safety Monitoring Board. There were no statistically significant differences between dose groups and no differences between first and second vaccinations in terms of reactogenicity. The majority of Adverse Events (AEs) were mild or moderate and only two subjects reported severe solicited AEs (headache and fatigue). The majority of solicited AEs resolved quickly. VLA2001 was found to be highly immunogenic with more than 90% of all study participants developing significant levels of antibodies to the

SARS-CoV-2 virus spike protein across all dose groups tested. In the high dose group which is the selected as the optimum dose, the GMT of neutralizing antibodies antibody titers measured 2 weeks after completion of the 2-dose schedule was at or above levels for a panel of convalescent sera.

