2.2 STATISTICAL HYPOTHESES

There are no formal statistical hypotheses in this study.

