2.4 TRIAL DESCRIPTION

This is a first-in-human phase I/II study that will evaluate three dose levels of VLA2001 (low, medium, high) for safety, tolerability and immunogenicity in a two-dose schedule in a healthy young adult population aged 18 to 55 years.

The study will be a combined open-label followed by a randomised, double-blind, dose-escalation, multicentre study with three dose groups (low, medium and high dose groups); 50 participants will be recruited to each dose group. The study is conducted in three parts: Part A (Day 1 to Day 36) and Part B (Day 37 to Day 208) followed by the Booster Phase: Part C (Visit 7 to Visit 10). Following an evaluation of Part A data (i.e. data up to Day 36) further clinical studies will be initiated. An additional data analysis will be performed during part B after all Participants have completed Visit 5 (Day 106).

The study will start with an open-label, staggered recruitment for the first 15 participants and subsequently in the blinded part of the study for all remaining 135 participants. Randomization will be done in 1:1:1 fashion for the 3 dose levels.

PART A:

For safety reasons, the first 15 participants will be included into the study in an open-label, not randomized manner following a staggered dose escalation of VLA2001. Dose escalation will be done at a single site to ensure permanent oversight on safety data by one principal investigator during the recruitment of the 15 sentinel participants.

Dose escalation starts with the first vaccination of the first sentinel participant in the low dose treatment group. After vaccination, the first participant of a dosing group will be observed for the development of any acute reaction at the study site for 3 hours after the vaccination procedure. Prior to discharge from the study site, vital signs will be measured and the participant will be instructed to use the eDiary. The next 4 participants of the same dosing group will be vaccinated at least with a one-hour interval between each participant. These 4 participants will be observed for 60 minutes at the study site to monitor for the development of acute reaction. Before discharge, vital signs will be measured and participants will be instructed to use their eDiaries. After confirmation by the investigator, the procedure will be repeated with the first participant of the next dose level. The minimum time before vaccination of a new dose level will be 48 hours.

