2.5 STUDY SAMPLE SIZE DETERMINATION

A total of 150 participants is considered sufficient to obtain initial safety data for VLA2001, especially since inactivated vaccines are a well-established, safe vaccine technology. Fifty participants per group will allow for 95% confidence that an AE with a true underlying incidence of about 2% would be observed in the present study.

In addition, assuming 10% of participants with protocol deviations, about 45 participants per dose group will be evaluable for immunogenicity. This sample size is in a range generally expected to allow selection of an appropriate dose level.

For the Booster Phase of this study, no formal sample size calculation has been performed and no minimal or maximal number of participants is defined. Based on operational considerations the total number of participants is expected to be up to approximately 80.

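### Differences in AE rates between doses are planned as p-values without an interval, so a non-significant result at 50 per arm does not show comparable safety

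*SAP*

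**What the plan says.** SAP 7.1.1 (solicited AEs) and 7.2.1 (unsolicited AEs) plan counts, percentages and exact Clopper-Pearson 95% CIs for each dose group and overall, together with summaries by severity. For the comparison between doses, 7.1.1 says: "Differences between the dose groups will be assessed for significance using Fisher-Freeman-Halton exact test and p-values will be presented for this test". Hochberg-adjusted pairwise Fisher p-values are calculated only when the overall test is significant. Protocol 16.4.1 and 16.4.3.1 describe the same two-stage testing. Neither they nor any title in the SAP table index (13.2) mention a risk difference, a risk ratio or a CI for a difference.

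The immunogenicity contrast is treated differently. Protocol 16.4.2 plans GMT ratios and least squares mean differences with 95% CIs, and SAP 8.1 repeats the differences and intervals.

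On use of the results, Protocol 8.5 states: "Based on the assessed comparable safety and superior immunogenicity results at Day 36, the high dose has been selected". Protocol 8.5.1, reporting the data to Day 36, states: "There were no statistically significant differences between dose groups", a sentence that goes on to limit itself to reactogenicity. The same paragraph cites no DSMB concern, mostly mild or moderate AEs, two participants with severe solicited AEs, and quick resolution.

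The design is openly descriptive. SAP 2.2 says: "There are no formal statistical hypotheses in this study". The protocol synopsis says: "No formal sample size calculation has been performed".

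**The concern.** Finding the optimal dose is a secondary objective (Protocol 9.3, SAP 2.1.2), and the decision weighs tolerability against immunogenicity. Only the immunogenicity side gets an effect estimate with an interval. On the safety side, a non-significant overall test ends the comparison, with no pairwise result of any kind. That is the very situation in which comparability is likely to be claimed, and the plan then displays nothing to show how large a dose-related increase in AEs remains compatible with the data. No margin is set either, so no planned test could establish similarity. A reader of the final report could take a failure to detect a difference as evidence that there is none.

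**Working it through.** **Inputs.** 50 participants per dose group and 150 in total (SAP 2.4, 2.5). Two-sided alpha of 0.05: SAP 7.1.1 gives no level, so this is borrowed from the same test in SAP 8.2.2. The documents give no AE rates by dose and no margin, so every rate and margin below is an assumption, shown over a range.

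**1. The plan's own figure.** SAP 2.5 says: "Fifty participants per group will allow for 95% confidence that an AE with a true underlying incidence of about 2% would be observed". The chance of at least one event is 1 − 0.98^n.
- n = 150: 1 − 0.98^150 = 0.952, which reproduces 95%.
- n = 50: 1 − 0.98^50 = 0.636, which does not.

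The size justification therefore concerns seeing an event somewhere in the whole study. It says nothing about comparing doses.

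**2. Power of a two-arm comparison.** Power is the sum of Bin(x; 50, p1) × Bin(y; 50, p2) over all tables (x, y) with two-sided Fisher p ≤ 0.05, by exact enumeration and without multiplicity adjustment.

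| Assumed true rates | Power |
|---|---|
| 2% vs 10% | 19% |
| 10% vs 20% | 20% |
| 30% vs 40% | 13% |
| 30% vs 45% | 27% |
| 30% vs 50% | 46% |
| 50% vs 70% | 46% |
| 10% vs 30% | 64% |
| 50% vs 80% | 85% |

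The difference detectable with 80% power is about 19 points from a base rate of 2%, 24.5 from 10%, and 28 to 29 from 20% to 50%.

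**3. Power of the planned overall test.** The same enumeration for the three-group Fisher-Freeman-Halton test gives 21% for 10/15/20%, 48% for 20/30/40%, and 42% for both 30/40/50% and 50/60/70%.

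**4. What an interval would show.** The Newcombe interval combines the two Wilson limits (l, u). With equal observed rates p, its half-width is √[(p − l)² + (u − p)²]. For 15/50 in both arms and z = 1.96:
- Wilson centre: (0.30 + 3.8416/100) / (1 + 3.8416/50) = 0.3384/1.0768 = 0.3143.
- Wilson half-width: 1.96 × √(0.30 × 0.70/50 + 3.8416/10,000) / 1.0768 = 0.1232.
- Limits: l = 0.1910 and u = 0.4375.
- Half-width for the difference: √(0.1090² + 0.1375²) = 0.175, or 17.5 points.

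The same calculation gives ±12.7 points at an observed 10% in both arms, ±15.7 at 20% and ±18.9 at 50%.

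With unequal counts, 15/50 versus 20/50 gives Fisher p = 0.40 and a score 95% CI for the difference of −8.7 to +27.9 points. A pairwise p-value would report only that no difference was significant.

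**5. Do the per-arm intervals fill the gap?** No. At 25/50 the Clopper-Pearson interval is 35.5% to 64.5%, or ±14.5 points. The difference between two such arms has an interval of ±18.9 points, so the uncertainty of the contrast cannot be read off one arm's interval.

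**The case against.** The strongest reply is that this is a descriptive first-in-human study with no formal hypotheses, so low power is expected and is not a fault. That stands. The issue is what may be inferred from non-significance, not the sample size.

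A reader might also infer three stronger things that the documents do not support.

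- **That safety is judged only by p-values.** It is not. Per-arm CIs, severity summaries, SAE and AESI tables and DSMB review all contribute. Only the formal contrast between doses lacks an estimate.
- **That comparable safety was concluded from non-significance.** Protocol 8.5 does not say how comparability was assessed. The non-significance statement is in another section, covers reactogenicity, and stands beside severity and DSMB findings. The Part A report is not among the documents. The link is reasonable because 8.5.1 offers no other between-dose evidence, but it remains an inference.
- **That the trial cannot support any such statement.** Counts and denominators by dose are planned output, so anyone can compute intervals for the differences. What is missing is their display and a rule for interpreting them.

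Two further points stand. The two-arm power figures are not the power of the planned sequence, which is why step 3 gives the overall test as well. And the Day 36 dose selection has already been made, so amending the SAP cannot alter it.

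**Conclusion.** The point holds in limited form. The planned contrast between doses for AE rates is a p-value alone, and with 50 per arm non-significance does not show comparability. Power is about 13% to 20% for a 10-point difference from base rates of 10%, 30% or 50%, and 46% to 64% for a 20-point difference from the same base rates. Equal observed rates between 10% and 50% leave about 13 to 19 points open in either direction. As a yardstick, with equal true rates of 10% to 50%, one-sided 0.025 and 80% power, excluding a 10-point excess would need 142 to 393 per arm; excluding a 20-point excess would need 36 to 99.

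These sizes rest on assumed rates and margins and on an alpha taken from another section of the SAP. They do not show that the doses differ in safety or that the dose decision was wrong. They show that the reported evidence does not by itself justify the word comparable. The change is worth making because it is cheap and affects what later reports can conclude.

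**What to change.** In SAP 7.1.1 and 7.2.1, add each pairwise risk difference with a 95% CI for any solicited local AE, any solicited systemic AE, any unsolicited AE and any related AE. Report these whatever the overall p-value, in all remaining and final outputs. Either a score or a Newcombe interval will do; name one in advance. The solicited AE tables (14.2.1.2 to 14.2.1.5) are not scheduled for the third interim analysis, so state that the Day 36 solicited data will be re-presented with these intervals.

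Base any comparability wording on the intervals. In Protocol 8.5, soften the safety claim to say that no significant difference was detected and that differences up to the confidence limits are not excluded.

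The cost is extra columns for four endpoints and three dose pairs (12 intervals), no new data, and a more guarded statement. The SAP should also say that the intervals are descriptive, because they can disagree with Fisher's test at the margin: 35/50 versus 25/50 gives p = 0.066 but a Newcombe interval of +0.8 to +37.2 points.

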7.2 ANALYSIS OF SECONDARY SAFETY ENDPOINTS

7.2.1 Unsolicited Adverse Events

All adverse events will be coded with Medical Dictionary for Regulatory Activities (MedDRA) version 23.1.

A participant with the same unsolicited AE with different reported relationships to study treatment will be summarized at the closest relationship. Also, a participant with the same AE at different severity grades will be summarized at the most severe grade.

An overall summary of adverse events will be presented by dose groups and overall and will include:

- Participants with any unsolicited AE until Day 36
- Participants with any unsolicited AE until Day 208
- Participant with any serious unsolicited AE until Day 36
- Participant with any serious unsolicited AE until Day 208
- Participant with any AESI until Day 36
- Participant with any AESI until Day 208
- Participants with any treatment related unsolicited AE until Day 36
- Participants with any treatment related unsolicited AE until Day 208
- Participants with any medically attended unsolicited AE until Day 36
- Participants with any medically attended unsolicited AE until Day 208

The following summaries of adverse events will be added for the additional interim analysis after Day 106. All adverse events collected up to the point of datacut will be presented.

- Participants with any unsolicited AE until day of Data Cut for Day 106 analysis
- Participant with any serious unsolicited AE until day of Data Cut for Day 106 analysis
- Participant with any AESI until day of Data Cut for Day 106 analysis
- Participants with any treatment related unsolicited AE until day of Data Cut for Day 106 analysis
- Participants with any medically attended unsolicited AE until day of Data Cut for Day 106 analysis

The follow-up time for participants until the point of data cut for the Day 106 analysis will be summarized.

The number and percentage of participants with unsolicited AEs along with the exact 95% Clopper-Pearson confidence interval (CI) for all AE rates will be presented for each dose group and overall. Differences between the dose groups will be assessed for significance using Fisher-Freeman-Halton exact test and p-values will be presented for this test. If overall group difference comes out to be significant then multiplicity adjusted p-values (using Hochberg method) for pairwise group difference will be calculated using Fisher's exact test.

In addition, following summaries will be presented by SOC and PT for each dose cohort and overall:

- Summary of unsolicited AEs until Day 36
- Summary of unsolicited AEs until Day 208
- Summary of serious unsolicited AEs until Day 36
- Summary of serious unsolicited AEs until Day 208
- Summary of AESI until Day 36
- Summary of AESI until Day 208
- Summary of treatment related unsolicited AEs until Day 36
- Summary of treatment related unsolicited AEs until Day 208

- Summary of unsolicited AEs by maximum severity
- Summary of unsolicited AEs by closest causality relationship

The following summaries of adverse events presented by SOC and PT will be added for the additional interim analysis after Day 106:

- Participants with any unsolicited AE until day of Data Cut for Day 106 analysis
- Participant with any serious unsolicited AE until day of Data Cut for Day 106 analysis
- Participant with any AESI until day of Data Cut for Day 106 analysis
- Participants with any treatment related unsolicited AE until day of Data Cut for Day 106 analysis
- Summary of unsolicited AEs by maximum severity until day of Data Cut for Day 106 analysis
- Summary of unsolicited AEs by closest causality relationship until day of Data Cut for Day 106 analysis

Participants with multiple adverse events within an SOC or SOC/PT combination are counted only once for that SOC or SOC/PT combination. For the summary table of AEs by maximum severity, if a participant experiences multiple events in the same SOC or SOC/PT combination, the highest recorded severity will contribute counts to the summary table. For the summary table of AEs by closest causality relationship, if a participant experiences multiple events in the same SOC or SOC/PT combination, the closest relationship to study drug will contribute counts to the summary table. All data from the adverse events eCRF will also be listed.

Booster Phase:

An overall summary of adverse events will be presented separately for the booster phase and will include:

- Participants with any unsolicited AE up to Visit 9 in the booster phase
- Participants with any treatment related unsolicited AE up to Visit 9 in the booster phase
- Participant with any serious unsolicited AE up to Visit 9 in the booster phase
- Participant with any AESI up to Visit 9 in the booster phase
- Participants with any unsolicited AE up to Visit 10 in the booster phase
- Participants with any treatment related unsolicited AE up to Visit 10 in the booster phase
- Participant with any serious unsolicited AE up to Visit 10 in the booster phase
- Participant with any AESI up to Visit 10 in the booster phase

In addition, following summaries will be presented by SOC and PT for the booster phase:

- Summary of unsolicited AEs up to Visit 9 in the booster phase
- Summary of treatment related unsolicited AEs up to Visit 9 in the booster phase
- Summary of serious unsolicited AEs up to Visit 9 in the booster phase
- Summary of AESI up to Visit 9 in the booster phase
- Summary of unsolicited AEs up to Visit 10 in the booster phase
- Summary of treatment related unsolicited AEs up to Visit 10 in the booster phase
- Summary of serious unsolicited AEs up to Visit 10 in the booster phase
- Summary of AESI up to Visit 10 in the booster phase
- Summary of unsolicited AEs by maximum severity up to Visit 9 in the booster phase

- Summary of unsolicited AEs by closest causality relationship up to Visit 9 in the booster phase
- Summary of unsolicited AEs by maximum severity up to Visit 10 in the booster phase
- Summary of unsolicited AEs by closest causality relationship up to Visit 10 in the booster phase

Adverse events that started in the booster phase will be presented separately in participant data listings.

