3.1.2 Secondary Endpoints

- Frequency and severity of any unsolicited AE until Day 36.
- Frequency and severity of any vaccine-related AE until Day 36.
- Frequency and severity of any AE until Day 208.
- Frequency and severity of any vaccine-related AE until Day 208.
- Frequency and severity of any SAE until Day 36.
- Frequency and severity of any AESI until Day 36.
- Frequency and severity of any SAE until Day 208.
- Frequency and severity of an AESI until Day 208.

Booster Phase:

- Frequency and severity of solicited AEs (local and systemic reactions) within 7 days after the booster vaccination
- Frequency and severity of any unsolicited AE up to Visit 9
- Frequency and severity of any vaccine-related AE up to Visit 9
- Frequency and severity of any SAE up to Visit 10
- Frequency and severity of any AESI up to Visit 10

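### SAP 7.2.1 lists SAE, vaccine-related AE and Day 208 AE rows for unsolicited events only, while the endpoints cover any such event; SAP 13.1 does not declare the restriction

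*SAP*

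**What the plan says.** SAP 3.1.2 repeats the 13 secondary safety endpoints of protocol 10.3.1.2: 8 for the primary series and 5 for the booster phase. Some are expressly limited, such as "Frequency and severity of any unsolicited AE until Day 36". Others carry no such limit. The SAE endpoint is worded "Frequency and severity of any SAE until Day 36", and the corresponding endpoint for events attributed to the vaccine is worded "Frequency and severity of any vaccine-related AE until Day 36". For the longer follow-up of all events the plan has "Frequency and severity of any AE until Day 208". The booster list follows the same pattern, for example with "Frequency and severity of any vaccine-related AE up to Visit 9".

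Protocol 16.4.3.1 names unsolicited AEs, related AEs, AESIs and SAEs as separate items to be presented overall, by system organ class and preferred term, and by severity.

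SAP 7.2 covers the analysis of the secondary safety endpoints and has a single subsection, on unsolicited AEs. Its row for serious events reads "Participant with any serious unsolicited AE until Day 36", while its row for events attributed to the vaccine reads "Participants with any treatment related unsolicited AE until Day 36". The AESI row carries no such limit: "Participant with any AESI until Day 36".

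Protocol 16.4 requires a change to the planned analyses to be described and justified in the SAP. SAP 13.1 declares one change, the dropped stratification by baseline serostatus.

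**The concern.** The endpoint list uses the word unsolicited in some places and not in others, so a reader will expect an SAE or related-AE count to cover solicited events too. Under the protocol's own rules the two scopes differ. Protocol 15.2.1.2 makes every solicited injection-site reaction causally related. Protocol 15.1.2 has Grade 4 solicited events reported as SAEs, and protocol 15.2.3 provides for serious solicited AEs.

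A row that counts only unsolicited events does not report the endpoint as defined. At stake is whether the related-AE and SAE figures in the study reports can be read as the protocol's endpoints.

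**Working it through.** The plan states no figure for this point, so the check is a comparison of text, followed by what it implies for the counts.

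**Endpoints against rows**

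| Endpoint in SAP 3.1.2 | Time points | Number | Rows in SAP 7 |
|---|---|---|---|
| Unsolicited AE | Day 36, Visit 9 | 2 | unsolicited: match |
| Booster solicited AE | 7 days | 1 | section 7.1.1: match |
| AESI | Day 36, Day 208, Visit 10 | 3 | not restricted: match |
| SAE | Day 36, Day 208, Visit 10 | 3 | serious unsolicited only |
| Vaccine-related AE | Day 36, Day 208, Visit 9 | 3 | related unsolicited only |
| Any AE | Day 208 | 1 | unsolicited only |

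Total: 2 + 1 + 3 + 3 + 3 + 1 = 13. Narrowed: 3 + 3 + 1 = 7.

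**Row count in SAP 7.2.1.** The blocks are the overall summary, the Day 106 overall summary, the SOC/PT summaries, the Day 106 SOC/PT summaries, the booster overall summary and the booster SOC/PT summaries.

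- Serious: 2 + 1 + 2 + 1 + 2 + 2 = 10, all unsolicited.
- Treatment related: 2 + 1 + 2 + 1 + 2 + 2 = 10, all unsolicited.
- The ten matching table titles (14.2.1.9, .10, .13, .14, .19, .21, .32, .33, .36 and .37) also say unsolicited.

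SAP 7.1.1 summarises solicited AEs by frequency and severity, and for the booster by duration. It does not summarise them by seriousness or relatedness, so it does not fill the gap.

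**Related AEs.** In a dose group, let u be the number of participants with a related unsolicited AE, l the number with a solicited injection-site reaction, and b the number with both. The row reports u. The endpoint is at least u + l − b. The shortfall is at least l − b, which cannot be negative, so the direction is fixed.

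The documents give no value of l for VLA2001. Protocol 8.1.2 gives only overall adverse-reaction rates for other candidates: 15.0% for one inactivated vaccine, and mostly above 60%, some 100%, for other platforms. Assumed for l purely as a scale, with 50 per group, these would be 0.15 × 50 = 7.5, above 0.60 × 50 = 30, and up to 50 participants, each less b. They are not local rates and not rates for this vaccine, so they do not estimate the shortfall.

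**SAEs.** A count changes only if a serious solicited AE occurs. As an illustration, take the expected booster size of about 80, one such event and no other SAE. The listed rows would show 0/80 (exact 95% CI 0 to 4.5%) instead of 1/80 (1.3%; 0.03 to 6.8%). The documents give no rate for such an event. Protocol 8.5.1 reports two participants with severe solicited AEs (headache and fatigue) up to Day 36 and describes neither as serious.

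**The case against.** The strongest counter-argument is that the table shells are not in the documents. The index in SAP 13.2 holds Table 14.2.1.1, an overall AE summary, beside Table 14.2.1.6, an overall summary of unsolicited AEs. In the booster text, a list introduced in the same way as the primary-series list belongs to Table 14.2.1.30, whose title says unsolicited. By analogy the primary-series list may belong to 14.2.1.6, leaving 14.2.1.1 free to be a combined table. SAP 12.1 also places table specifications after the SAP. This stands: a reader might infer that the primary series will have no combined summary, and the documents do not establish that. What they establish is that no combined row is specified. The booster phase has no comparable table: 14.2.1.30 is its only overall table, and 14.2.1.1 is indexed for the main safety set.

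The unrestricted AESI rows might seem to prove that the restriction elsewhere is deliberate. That is weak evidence, since none of the solicited terms appears in the AESI list of protocol 22.5.

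A reader might also infer that SAEs could be concealed. The documents do not support this. A serious solicited AE would still reach the listings (Listing 16.2.1.1 covers solicited AEs from the AE eCRF), expedited SAE reporting and the DSMB, and a related SAE suspends vaccination pending DSMB review under protocol 10.6.2.

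It is also fair that the ten table titles state their scope, that solicited rates appear separately with exact confidence intervals, that SAP 2.2 sets no formal hypotheses, and that the dose was chosen on Day 36 data (protocol 8.5). These points limit the consequence. They do not make an unsolicited-only row equal to an endpoint defined for any event, or supply the missing declaration.

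**Conclusion.** The mismatch holds for seven of the 13 secondary safety endpoints and is not declared. It is definite for the booster phase. For the primary series it is a gap in the SAP text that Table 14.2.1.1 may or may not close.

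For related AEs the effect has a certain direction and an unknown size. What is missing is the combined rate, not the local reaction data. For SAEs the effect is conditional on an event that is not documented. A percentage range for the participants left out should not be read from the rates quoted for other vaccines.

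This is a minor to moderate correction. Confidence is high for the text mismatch and low for the size of its effect.

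**What to change.** - In SAP 7.2.1, state that Table 14.2.1.1 has rows for any AE, any SAE and any vaccine-related AE over solicited and unsolicited events combined, until Day 36 and until Day 208. Give them overall and by maximum severity, because the endpoints are frequency and severity.
- Add a booster counterpart: any SAE up to Visit 10 and any vaccine-related AE up to Visit 9.
- Count solicited injection-site reactions as related. Protocol 15.2.3 provides detailed causality assessment only for solicited AEs that are serious or medically attended, so state whether the protocol 15.2.1.2 default, under which missing causality counts as related, applies to the other solicited systemic AEs.
- Keep the unsolicited-only rows and the SOC/PT tables as a breakdown, so that local reactions do not mask a related unsolicited signal, and record their scope in SAP 13.1. A note in 13.1 alone would cure the missing declaration but leave the endpoints unreported as defined.

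The cost is SAP wording, rows in one indexed table, one new booster table and one decision on causality, from data the plan already collects. The combined rates may look higher than the unsolicited-only ones. Part A has already been analysed, so the Day 36 combined rows would come in a later report.
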